### **4. Study Endpoints**

The primary and secondary endpoints are as follows:

The primary endpoint is the mean increase in gait speed demonstrated during the 10MWT after 12 weeks/ 36 sessions of training and compared between groups. Both self-selected and fast speeds will be performed on the 10MWT, with the fast speed taking precedent.

The secondary endpoints of Participant outcomes related to physical performance, physiology, quality of life, and safety are to be measured at week 6/following 18 sessions (midpoint), week 12/following 36 sessions (primary endpoint), and week 24/3 months after the last session (follow-up) (unless otherwise indicated) and compared between groups.

By category, these are the following:

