**SECONDARY COMPLICATIONS**

International SCI Pain Basic Data Set

Numeric Pain Rating Scale for self-reported neuropathic pain upon resting and during gait training  
SCATS, Modified Ashworth Scale, patient-report SCI-SET, and Numeric Rating Scale for spasticity

Modified International SCI Bowel Function Basic Data Set

Modified International SCI Lower Urinary Tract Basic Data Set

Incidence of urinary tract infections per Participant

Incidence of pressure ulcers per Participant

Incidence of falls per Participant

Incidence of re-hospitalization/unexpected doctor visits per Participant

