If the participant continues to meet criteria for this study the following data will be collected as *baseline data*. **NOTE: All Participant evaluations are conducted outside of Ekso, BWSTT, or BWS for overground walking. Baseline examinations may not occur more than 30 days prior to initiation of the training regimen:**

1. 10 Meter Walk Test (10MWT), at both self-selected and fast speeds
2. GAITRite Pressure Map for Temporospatial Gait Parameters (if site has one)
3. Timed Up and Go (TUG)
4. 6 Minute Walk Test (6MWT)
5. Spinal Cord Injury Functional Ambulation Inventory (SCI-FAI)
6. Walking Index for Spinal Cord Injury (WISCI II)
7. Upper and Lower Extremity Muscle Strength
8. Berg Balance Scale
9. The Spinal Cord Assessment Tool for Spastic Reflexes (SCATS)
10. Spinal Cord Independence Measure III (SCIM-III), Mobility subscale only, by interview
11. Modified Ashworth Scale
12. Spinal Cord Injury Spasticity Evaluation Tool (SCI-SET)

13. Numeric Rating Scale for spasticity
14. International SCI Quality of Life Basic Data Set
15. Epidemiological Studies Depression Scale (CES-D 10)
16. Borg Scale for maximal Rate of Perceived Exertion (collected at baseline 6MWT and at training session 1)
17. International SCI Pain Basic Data Set
18. Modified International SCI Bowel Function Basic Data Set
19. Modified International SCI Lower Urinary Tract Basic Data Set

See Appendix A for description of assessments.

The following data will be collected *per session*:

1. Any adverse events/complications (related to Participant or staff) noted following prior training session and during present session
2. Assessment of skin integrity of the anterior and posterior torso, anterior tibia, sacral area and bilateral feet (before and after training)
3. Walk time\*
4. Stand time\*
5. Seated rest time
6. Number of steps total and in each mode\* or number of steps at each BWS%
7. Time spent in each mode\* or time spent at each BWS%
8. Any equipment used for training, including type of assistive device and braces
9. Number of therapists/staff required at each training session to ensure the safety of the Participant and to complete the training session goals
10. Amount of assistance (e.g. min, mod, max) as reported by staff members at each training position (hips, trunk, right LE, left LE, etc.)

\* For Group 1 Participants, these data are *automatically collected* by Ekso (in Ekso Pulse) at the end of each training session

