Assessment	Screening  Visit  (may be used for baseline data if done over 1-2 days)	Baseline  Visit  Week 0 (Not > 30 days prior to first training session)	Session Assessments GROUPS 1 & 2  (and Run-In  ) Sessions 1-36 No braces for 10MWT			Evaluations ALL GROUPS (including Run-In) After session 18** (Week 6) Midpoint (+/- 1 week of completing session 18) Braces OK for walking tests	Evaluations ALL GROUPS (including Run-In) After session 36** (Week 12) Endpoint (+/- 1 week of completing session 36) Braces OK for walking tests	Evaluations GROUPS 1 & 2 only (Not Run-In or Group 3 Participants) 3 months following the last training session** (Week 24) Follow-Up, (+/- 3 weeks) Braces OK for walking tests
			B 	D 	A 			
Berg Balance Scale		✓				✓	✓	✓
10 Meter Walk Test  (self-selected and fast)	✓	✓ (both with and without braces)	✓ 			✓ (baseline + current device/braces)	✓ (baseline + current device/braces)	✓ (baseline + current device/braces)
Timed Up & Go (TUG) 		✓				✓	✓	✓
6 Minute Walk Test 		✓				✓	✓	✓
SCI-FAI		✓				✓	✓	✓
WISCI II 		✓				✓	✓	✓
SCIM-III, Mobility subscale only		✓				✓	✓	✓
SCI-SET		✓				✓	✓	✓
Numeric Rating Scale (for spasticity)		✓ (after 1st session)		✓ 				
International SCI Quality of Life Basic Data set		✓				✓	✓	✓
Epidemiological Studies Depression Scale (CES-D 10)		✓				✓	✓	✓
Borg - Maximum during training and 6MWT		✓ (during baseline 6MWT and after 1st session)		✓ 		✓	✓	✓
NASA- Task Load Index		✓ (after 1st session)		✓ 				
International SCI Pain Basic Data Set		✓				✓	✓	✓
Numeric Pain Scale † (for neuropathic pain )		✓ (after 1st session)	✓ 	✓ 				

Assessment	Screening  Visit  (may be used for baseline data if done over 1-2 days)	Baseline  Visit  Week 0 (Not > 30 days prior to first training session)	Session Assessments GROUPS 1 & 2  (and Run-In) Sessions 1-36			Evaluations ALL GROUPS (including Run-In) After session 18 Week 6** Midpoint (+/- 1 week of completing session 18)	Evaluations ALL GROUPS (including Run-In) After session 36 Week 12** Endpoint (+/- 1 week of completing session 36)	Evaluations GROUPS 1 & 2 only (Not Run-In or Group 3 Participants) Week 24** Follow-Up, 3 months following the last training session (+/- 3 weeks)

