**Footnotes (Table 2):**

† Height may be obtained verbally; weight must be measured via scale. Calculate BMI using NIH National Heart Lung and Blood Institute calculator at: [http://www.nhlbi.nih.gov/health/educational/lose\\_wt/BMI/bmicalc.htm](http://www.nhlbi.nih.gov/health/educational/lose_wt/BMI/bmicalc.htm)

\* Skin assessment to be performed before and after training sessions

• Maximum Borg to be done during session 1 then during weekly sessions (every third session) thereafter, and after 6 minute walk test during evaluations

\*\* Assessments to be performed outside of exoskeleton or any body weight support and on a non-training day.

◦ Vital signs (BP and HR) will be measured as follows:

- °° Upon relaxation (5 minutes) in sitting position after arrival. After 1 minute of standing (may hold on to something for balance or use standing in frame as needed)
- °°° Vitals should be taken in sitting before and immediately after 6 minute walk
- ↳ To be taken prior to 10MWT
- " To be taken prior to each session and needed only if orthostatic hypotension was present at the time of the previous session and/or if symptomatic upon standing at the time of the current session.

♦ Run In will follow Group 1 assessments but will not complete the follow up evaluation visit and assessments

^ To be obtained during Screening, and if participant passes screening can be used for Baseline

† Numeric Pain Scale: to be completed before and during session 1 and weekly thereafter

¤ To be done by blinded evaluator for comparison to week 6, 12, 24 (midpoint, endpoint, and follow-up) evaluation visit results.

☆ Done by blinded evaluator for comparison. Testing to be done according to ISNCSCI instructions (supine, using the correct limb positioning and angles for resistance)

 May occur over one or two visits

 B = before session, D = during session, A = after session

 Passive Group 3 will complete all evaluations at Baseline, Week 6 and week 12, the same as Groups 1 and 2, then have the option (per participant decision) to undergo 12 weeks of training using the exoskeleton or standard gait training. The optional 12 week period will consist of training only. No further evaluations will be completed at this time.

Update Concomitant Medication Log accordingly

To include shoulder flexion/extension, abduction/, and triceps

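### The numeric spasticity and pain scales are scheduled only around training sessions, so they cannot be compared with passive control or at week 24, and their baseline timing is inconsistent.

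*Protocol*

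**What the plan says.** **Endpoints.** Protocol Section 4 sets the secondary endpoints at the midpoint, week 12 and week 24 ("unless otherwise indicated) and compared between groups"). Under secondary complications it lists "SCATS, Modified Ashworth Scale, patient-report SCI-SET, and Numeric Rating Scale for spasticity", and separately a numeric scale for neuropathic pain at rest and during gait training. SAP 1.1 names numeric rating scales among the ordinal data meant for repeated-measures modelling.

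**Baseline list.** Section 11, item 13 of the baseline data, reads "Numeric Rating Scale for spasticity", with no reference to a session or a group. The pain scale is not in that list. Item 16 (Borg) does carry a session-1 qualifier.

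**Table 2.** The rows "Numeric Rating Scale (for spasticity)" and "Numeric Pain Scale † (for neuropathic pain)" each have a baseline tick marked "after 1st session". Their other ticks are under "Session Assessments GROUPS 1 & 2" (and run-in), at every third session. Neither row is ticked at the week-6, week-12 or week-24 evaluations.

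**Footnotes.** The pain footnote reads "Numeric Pain Scale: to be completed before and during session 1 and weekly thereafter". Footnote 3 gives Group 3 the evaluations at baseline, week 6 and week 12, followed by optional training with no further evaluations.

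**The concern.** An endpoint that is compared between groups needs values in those groups. For these two scales the schedule follows the training sessions, and the passive arm has none during its 12 weeks of observation. The comparison with no training shows whether gait training of either kind changes spasticity or pain at all. Ekso versus active control cannot answer that, because both arms train.

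The reference value is also unsettled. A site following the Section 11 list would rate spasticity at the baseline visit, and a site following Table 2 would rate it after the first training session. Pooled data would then mix pre-training and post-session reference values.

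**Working it through.** No sample size, power or alpha figure is at issue. The check is a count of scheduled occasions in each arm, followed by a comparison of the baseline instructions.

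**1. Groups 1 and 2.** Inputs: 36 sessions (Section 10), a rating at session 1 (Table 2), and a rating at every third session (Section 11).
- Every-third-session ratings: 36 / 3 = 12.
- With session 1: 1 + 12 = 13 occasions.
- 18 = 6 × 3 and 36 = 12 × 3, so ratings fall at sessions 18 and 36, next to the midpoint and endpoint evaluations.
- Week 24: 0 occasions.

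**2. Group 3.** Inputs: Table 2 and its footnote 3.
- Session columns: 0, since they cover Groups 1, 2 and run-in only.
- Baseline tick: 0 usable, since it is tied to a first session that Group 3 does not have before week 12.
- Weeks 6 and 12: 0, since neither row is ticked.
- If the Section 11 list is followed instead of Table 2, there is at most 1 value: spasticity, at baseline.
- Post-baseline values: 0 on either reading.

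**3. Share of the trial affected.** Under 2:2:1 allocation the passive arm is 1 / (2 + 2 + 1) = 1/5.
- Evaluable sample: 95 / 5 = 19.
- Maximum enrolment: 127 / 5 = 25.4, about 25.

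**4. Contrasts for each scale during the 12 weeks.**

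| Contrast | Available? |
|---|---|
| Ekso vs active control | Yes, from session ratings |
| Ekso vs passive control | No |
| Active vs passive control | No |

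Two of three pairwise contrasts are lost. At week 24, where Table 2 schedules only Groups 1 and 2, the remaining contrast is lost too.

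**5. Baseline instructions side by side.**

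| Scale | Section 11 baseline list | Table 2 | Table 2 footnote |
|---|---|---|---|
| Spasticity | Baseline item, no session qualifier | After first session | None on timing of the first rating |
| Pain | Not listed | After first session | Before and during session 1 |

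Section 10 (rule 2) and Table 2 footnote 8 put the first training session on a different occasion from the baseline visit. A tick in the baseline-visit column therefore cannot also fall after session 1. For spasticity the list and the table conflict; for pain the table and its own footnote conflict.

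**The case against.** The strongest defence is that Section 4 allows exceptions to its measurement times, and Table 2 may be that exception. This could explain the different timing. It does not explain the missing arm. Where the protocol means the trained arms only, it says so: staffing is specified for Groups 1 and 2, and Borg is tied to the interventions. The spasticity scale has no such limit. It stands beside SCATS, the Modified Ashworth Scale (MAS) and SCI-SET, all of which are ticked for every group at weeks 6 and 12. For pain the defence is partly right, because pain during gait training cannot exist in Group 3. Only resting pain is at issue there.

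A reader might infer more than the documents support:

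- **That no between-group comparison is possible.** Ekso versus active control remains available, including at sessions 18 and 36. Change from baseline is not specified for these scales, so it cannot be called the planned analysis.
- **That Group 3 has no values at all.** This is true under Table 2, but the Section 11 list would give it a spasticity baseline.
- **That the reference value is contaminated by training, so that a first-session effect is subtracted in full.** The pain footnote provides a rating before session 1. Appendix A defines the numeric scale by recall over the past week, so a spasticity score given after one session still largely reflects untrained days. The documents give no figure for a first-session effect.

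It also stands that the domains are covered elsewhere. MAS, SCATS, SCI-SET and the International SCI Pain Basic Data Set are scheduled at baseline, week 6 and week 12 in all groups, and at week 24 in Groups 1 and 2.

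**Conclusion.** The point holds as a minor scheduling defect with an inconsistent baseline. As written, two listed secondary endpoints have no post-baseline data in one fifth of the randomised participants and no week-24 data in anyone. The conclusion assumes that the Table 2 ticks are complete as printed and that Group 3 has no sessions before its week-12 evaluation. It does not depend on which baseline instruction sites follow.

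The primary endpoint, its two tests and the sample size are unaffected. Spasticity and pain can still be compared with passive control through the other four instruments. What is lost is the numeric self-rating in that comparison and at follow-up.

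**What to change.** 1. Reconcile the Section 11 baseline list, Table 2 and the pain footnote on one baseline taken before any training.
2. In Table 2, add the spasticity scale and resting pain, but not pain during training, to the baseline, week-6 and week-12 evaluations for all groups, and to week 24 for Groups 1 and 2.
3. Keep the session-1 and every-third-session ratings as monitoring within Groups 1 and 2.
4. If the added ratings are not wanted, state in Section 4 that these two endpoints compare Groups 1 and 2 only and have no week-24 value.

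**Cost.** A protocol table edit, plus self-report time at visits already planned. Appendix A puts both scales together at no more than 5 minutes. That is at most 3 × 5 = 15 minutes per participant in Group 3 and 4 × 5 = 20 minutes in Groups 1 and 2 over the whole study. Step 4 adds no participant time but gives up the passive-arm comparison and the week-24 value on these scales.

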**Footnotes (Table 2):**

† Height may be obtained verbally; weight must be measured via scale. Calculate BMI using NIH National Heart Lung and Blood Institute calculator at: [http://www.nhlbi.nih.gov/health/educational/lose\\_wt/BMI/bmicalc.htm](http://www.nhlbi.nih.gov/health/educational/lose_wt/BMI/bmicalc.htm)

\* Skin assessment to be performed before and after training sessions

• Maximum Borg to be done during session 1 then during weekly sessions (every third session) thereafter, and after 6 minute walk test during evaluations

\*\* Assessments to be performed outside of exoskeleton or any body weight support and on a non-training day.

◦ Vital signs (BP and HR) will be measured as follows:

- °° Upon relaxation (5 minutes) in sitting position after arrival. After 1 minute of standing (may hold on to something for balance or use standing in frame as needed)
- °°° Vitals should be taken in sitting before and immediately after 6 minute walk
- ↳ To be taken prior to 10MWT
- " To be taken prior to each session and needed only if orthostatic hypotension was present at the time of the previous session and/or if symptomatic upon standing at the time of the current session.

♦ Run In will follow Group 1 assessments but will not complete the follow up evaluation visit and assessments

^ To be obtained during Screening, and if participant passes screening can be used for Baseline

† Numeric Pain Scale: to be completed before and during session 1 and weekly thereafter

¤ To be done by blinded evaluator for comparison to week 6, 12, 24 (midpoint, endpoint, and follow-up) evaluation visit results.

☆ Done by blinded evaluator for comparison. Testing to be done according to ISNCSCI instructions (supine, using the correct limb positioning and angles for resistance)

 May occur over one or two visits

 B = before session, D = during session, A = after session

 Passive Group 3 will complete all evaluations at Baseline, Week 6 and week 12, the same as Groups 1 and 2, then have the option (per participant decision) to undergo 12 weeks of training using the exoskeleton or standard gait training. The optional 12 week period will consist of training only. No further evaluations will be completed at this time.

Update Concomitant Medication Log accordingly

To include shoulder flexion/extension, abduction/, and triceps

Skin assessment with focus on back, sacrum, shins, and feet to be collected before and after each training session

To be collected outside of the exoskeleton or any body weight support, and prior to any training session; can be used to assess readiness to transition to overground training weekly.

**Screening:** (10MWT) 1 walk with or without braces at self-selected speed to confirm qualification self-selected speed of <0.44 m/s. A second trial may should be done if first trial is close to 0.44 m/s.

**Baseline:** up to 8 trials (total) of 10MWT (2 trials each, with and without braces at both self-selected and fast speeds (to be done by blinded evaluator)

**Every 3rd session:** 10MWT (2 trials, without braces at self-selected speed), every 3rd session, if possible. The walk is done without braces (to determine neurological recovery changes). Pt can complete second walk to donn Ekso, or to donn the harness for BWSTT (depending on randomization and tolerance).

**Evaluations** at 6, 12, 24 weeks (midpoint, endpoint, and follow-up): up to 8 trials (total) of 10MWT (2 trials each, with **baseline** device/braces at both self-selected and fast speeds, then 2 trials with **current** device/braces at self-selected and fast speeds, performed with whatever assistive devices are needed for safe ambulation (to be done by blinded evaluator)

The first training in the exoskeleton occurs separately from screening and baseline data collection

Form to be completed at the time of study completion or at any time of early termination

Use baseline assistive device(s) and brace(s) for all TUG and 6 MWT assessments.

Every 3rd session

Score WISCI for current device/braces at self-selected speed

Table 3 - Therapist Assessments, and Data Collection Intervals (to be completed by the lead treating PT). Report of pain/injury to be completed by all participating session staff	Baseline Visit After 1 st Session	Session Evaluations GROUPS 1 & 2 (and Run-In) Sessions 1-36			Evaluations ALL GROUPS (including Run-In) After session 18** (Week 6) Midpoint (+/- 1 week of completing session 18)	Evaluations ALL GROUPS (including Run-In) After session 36** (Week 12) Endpoint (+/- 1 week of completing session 36)
Assessment		B	D	A		
NASA – Task Load Index, therapist physical load***	✓ (after 1st session)			✓		
Video assessment of posture during training ○	✓ (after 1st session)		✓*			
Borg Perceived Exertion (in each training environment) **	✓ (after 1st session)		✓			
Therapist/staff report of pain and/or injury ****	✓			✓		

\*During first and last sessions only (sessions #1 and #36)

○ Video of session # 36 should be taken at the same general point as session #1 as noted on source document.

\*\* During session 1 and every 3rd session thereafter (starting with session 3)

\*\*\* After session 1 and every 3rd session thereafter (starting with session 3)

\*\*\*\* Baseline upon registration for ID in EDC (before first session) and every session thereafter . To be completed by all staff participating in a treatment session.

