The following data will be collected *at every 3rd session* (i.e. session 3, 6, 9, etc.,(refer to Table 2):

1. 10MWT without braces at self-selected speed
2. Borg Scale for maximal RPE during intervention and overground training
3. Numeric Pain Rating Scale of neuropathic pain during rest and during the intervention
4. Numeric Rating Scale for spasticity
5. NASA – Participant Task Load Index
6. Heart rate and blood pressure

Therapist assessments include the following:

1. NASA-Task Load Index
2. Video Assessment of therapist posture during sessions 1 and 36
3. Borg Scale for maximal RPE during intervention and overground training
4. Reports of injuries or pain (includes all treating staff)

Table 2 shows the list of Participant assessments and data collection intervals. Therapist measures are included in Table 3.

Table 2 - Participant Assessments and Data Collection Intervals	Screening Visit	Baseline Visit	Session Assessments GROUPS 1 & 2 (and Run In) Sessions 1-36			Evaluations ALL GROUPS (including Run In) After session 18 Week 6** Midpoint (+/- 1 week of completing session 18)	Evaluations ALL GROUPS (including Run In) After session 36 Week 12** Endpoint (+/- 1 week of completing session 36)	Evaluations GROUPS 1 & 2 only (Not Run-In or Group 3 Participants) Week 24** Follow-Up, 3 months following the last training session (+/- 3 weeks)
	Assessment		Week 0 (Not > 30 days prior to first training session)	B	D	A		
Physician Clearance		✓						
Demographics ^	✓							
Medical History ^	✓							
Concomitant Medications 	✓	✓	✓			✓	✓	✓
BMI ^‡	✓	✓				✓	✓	✓
Vital Signs °^	✓°°	✓°°°	✓°°			✓°°°	✓°°°	✓°°°
ROM: Hip, Knee, Ankle ^	✓							
UE MMT  ^	✓							
Skin Assessment 	✓	✓	✓	✓				
Modified Ashworth Scale	✓	✓¤				✓	✓	✓
SCATS		✓				✓	✓	✓
UEMS	✓	✓☆				✓☆		✓☆
LEMS	✓	✓☆				✓☆		✓☆
Full ISNCSCI Exam ^	✓						✓	

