## **23.      Potential Risks to Study Participants and Mitigation of Risks**

- 1) The risk of falling: Having experienced therapists conduct the training sessions will minimize the risk of falling.
- 2) Risk of exceeding range of motion: This would be caused if any device moves the Participant beyond the normal range of motion, resulting in a strain, sprain or fracture. For the Ekso device, this risk is lessened by mechanical hard stops that prevent the device from exceeding a normal human range of motion even in the event of an electrical or software failure. Software systems are also in place to further reduce range of motion to improve fit and comfort during walking. Participants will be evaluated by clinicians who will eliminate Participants from being included in the study if Participants cannot meet the required range of motion. For all other devices, this risk will be mitigated through proper settings by the physical therapist in charge of Participants treatment.
- 3) Discomfort, skin pressure/friction, bruising, pain, or unusual swelling caused by any device that contacts the skin. This risk will be minimized by a thorough skin check performed by experienced personnel at each training session. Adjustments to the harness placement and additional padding will be assessed to decrease the risk of skin breakdown as well.
- 4) Blood pressure instability related to standing or activity. This risk will be reduced by checking blood pressure and heart rate prior to training, and as necessary during training and after.
- 5) Reflex bowel or bladder activity or autonomic instability during walking. This risk will be minimized by requiring Participants to relieve bowels and bladder prior to walking.
- 6) Spasms triggered by joint movement in the device. This risk will be reduced through screening prior to enrollment in the study. Participants cannot take part if the Participant's muscles are too stiff.
- 7) Any device used during this study could malfunction. In the event of device malfunction, Participants will be able to safely transfer out of the device.
- 8) There is a risk of fractures when participating in a therapy program: this will be minimized by requiring medical clearance if Participants are at risk for severe osteoporosis.

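### Section 23 relies on a blood pressure and heart rate check before training, but Section 11 makes that check conditional at 24 of 36 sessions, including the first two, with a trigger that often has no reading behind it

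*Protocol*

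**What the plan says.** Three parts of the Protocol bear on vital signs before training.

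- **Section 23, risk 4**, on unstable blood pressure when standing or active, says: "This risk will be reduced by checking blood pressure and heart rate prior to training, and as necessary during training and after". It attaches no condition to the pre-training check and gives no frequency. Risk 3 in the same section does give one for the skin check: "thorough skin check performed by experienced personnel at each training session".
- **Section 11, data lists.** "Heart rate and blood pressure" is the last item in the list for every third session. The ten-item list for every session includes the skin check but has no blood pressure or heart rate item.
- **Section 11, Table 2 footnotes.** One vital-signs note places the reading ahead of the 10 Meter Walk Test (10MWT), which during training is done at every third session. The next note says: "To be taken prior to each session and needed only if orthostatic hypotension was present at the time of the previous session". A second trigger, which may apply alone or together with the first, is a participant who has symptoms when standing that day. The sit/stand reading is described as "Upon relaxation (5 minutes) in sitting position after arrival. After 1 minute of standing". For the 6-minute walk the rule is: "Vitals should be taken in sitting before and immediately after 6 minute walk".

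**The concern.** Section 23 names a risk and tells the reader how it is controlled. If the schedule in Section 11 does not deliver that control, either the risk section overstates the protection or the schedule understates the procedure.

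The weak place is the start of training. At session 1 there is no previous session for the trigger to look back on. At session 2 the previous session is one at which no routine reading was required. The symptom trigger works at both, but by construction it cannot catch a fall in pressure that the participant does not feel.

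The last required standing reading before training is the sit-to-stand measurement at screening. The baseline readings around the 6-minute walk are seated, baseline may be up to 30 days before training starts, and the first training session must fall on a different day from screening and baseline. At stake is a participant with a symptom-free drop who begins upright training without the check that risk 4 describes.

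**Working it through.** **Inputs.** Training sessions: 3 per week × 12 weeks = 36, which matches the Protocol's stated total (Section 10, rule 1). Routine readings: every third session (Section 11). Conditional rule: Table 2 footnotes. Duration of a sit/stand reading: 5 minutes seated + 1 minute standing = 6 timed minutes. The Protocol gives no total number of vital-sign checks, so there is no stated count to reproduce.

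**Step 1: the schedule that Section 11 sets.**
- Routine: 36 / 3 = 12 sessions (3, 6, ..., 36), in line with the 10MWT.
- Conditional: 36 − 12 = 24 sessions (1, 2, 4, 5, ..., 34, 35).

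**Step 2: what lies behind the previous-session trigger at those 24 sessions**, for a participant without symptoms.

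| Conditional sessions | Count | Required reading at the previous session? |
|---|---|---|
| 1 | 1 | No previous session |
| 2, 5, 8, ..., 35 | 12 | No |
| 4, 7, ..., 34 | 11 | Yes (routine) |
| Total | 24 | |

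Without a required reading: 1 + 12 = 13 of 24.

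**Step 3: the favourable bound.** The footnote does not define orthostatic hypotension. Exclusion 21, which concerns the uncontrolled or severe form, describes it as a symptomatic drop. If the footnote uses the term that way, symptoms at the previous session would themselves have required a reading there. Only session 1 is then left, so the count is 1 of 24.

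**Step 4: the schedule after the fix.**
- Routine: 12 + 1 = 13 sessions (1, 3, 6, ..., 36).
- Conditional: 36 − 13 = 23 sessions, all with a last recorded reading to refer to. The new trigger wording achieves this; the session 1 reading makes the reference recent.
- Longest run of conditional sessions: 2 (4 and 5, 7 and 8, and so on).
- Added time: 1 × 6 = 6 minutes per participant.

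**The case against.** The strongest reply is that Section 11 is coherent. The note tying the reading to the 10MWT, the every-third-session list and the absence of the item from the per-session list all point to one schedule: routine with the walk test, conditional otherwise. That stands, and the counts above use that schedule.

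A reader might go further and infer that the Protocol holds several competing rules, with anything from 12 to 36 required checks. The documents do not support 36. Risk 4 states no frequency, and the contrast with risk 3 counts against reading it as every session. The pre-session tick in the Table 2 vital-signs row shows no every-third-session limit, but its symbols may have been altered in extraction: the marks for the two timing notes appear on no cell of that row.

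A reader might also infer that sessions 1 and 2 have no check at all. That is too strong. Only the routine check is missing; symptoms on standing require a reading at any session.

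Existing safeguards also count: a sit-to-stand pressure at screening, physician clearance, inclusion 11, exclusion 21, and the further checks during and after training that risk 4 allows as needed. They are not complete. Inclusion 11 can be met by taking part in a standing program, and exclusion 21 bars only uncontrolled or severe cases that limit standing. The documents give no event rate, so no harm can be quantified.

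**Conclusion.** The point holds as a mismatch between Sections 11 and 23 and a defect in one trigger. Section 11 requires 12 routine checks and leaves 24 sessions conditional, while risk 4 presents the pre-training check without a condition. The previous-session trigger is empty at session 1. For symptom-free drops it lacks a required reading at 13 of 24 conditional sessions, or at 1 of 24 under the symptomatic definition.

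The conclusion assumes that the every-third-session reading is taken both sitting and standing (the Section 11 list states no posture) and that Section 11, not the risk summary, sets the schedule. It does not depend on the Table 2 tick.

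This is a minor safety-procedure correction. It does not bear on the primary endpoint, power or the comparison between arms, and nothing in the documents shows that symptom-triggered checks have failed.

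**What to change.** Make three wording changes:

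1. In Section 11, require blood pressure and heart rate, sitting and then after 1 minute of standing, before session 1.
2. In the Table 2 footnote, base the hypotension trigger on the last recorded reading instead of the previous session. Keep the symptom trigger.
3. In Section 23, reword risk 4 so that it describes this rule.

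The cost is one added reading, about 6 minutes per participant. It falls within the 75 − 45 = 30 minutes between session length and the recommended slot, although that time also covers donning and set-up. One limit remains: a new symptom-free drop could still pass two sessions, such as 4 and 5, before the next routine check.

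A reading before every session would close that gap. It means 24 more readings than now, or 24 × 6 = 144 minutes per participant. That is a choice for the sponsor, not a required correction.
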